**Figure 7**

The advantage of this multi-epitope TARP peptide vaccine platform is that the overlapping epitopes cover the entire TARP protein, eliminating the need for HLA restriction in study participants that will greatly facilitate the rate of study accrual. In addition, these longer synthetic peptides include MHC class II CD4+ T cell helper epitopes that will allow generation of better CD8+ T cell responses with improved functional avidity and longevity (42) as well as humoral anti-TARP antibody responses.

#### 1.2.6 Rationale for Proposed Phase II Study Design

The rationale for the current phase II study design is to definitively establish that the observed declines in the difference in the slope log (PSA) documented in our initial pilot 09-C-0139 TARP study are indeed real and not due to spontaneous or random slowing in the rate of PSA rise. The observed decreased PSA slope in over 70% of all the patients with a vaccine that has no clinically significant adverse effects other than mild local injection site reactions (<Grade II) is an extremely promising result for any cancer therapy that needs to be confirmed in a prospective, randomized study. Therefore, it is essential to carry out a randomized, placebo-controlled phase II study. However, to accrue a large enough population for such a randomized phase II study, enrollment cannot be restricted to HLA-A2 positive patients and the excessive screening that entails. We must be able to include patients of all HLA types. We therefore propose to expand the vaccine platform coverage to include the whole TARP protein, as has been done for other tumor antigens like PSA, CEA, and melanoma antigens in the CCR and elsewhere once the value of the antigen target was demonstrated first in HLA-A2 positive patients. (31-38) The whole protein will have all the possible epitopes that can be presented by any HLA molecule and therefore would be suitable for vaccinating the entire population of prostate cancer patients,

making adequate accrual feasible. For the reasons stated earlier, overlapping long peptides such as the 20-mers overlapping by 10 residues have been widely used to represent a whole protein because they contain all the potential epitopes of the whole protein but are more amenable to processing for both class I and class II HLA presentation to CD4+ and CD8+ T cells. (13, 39-41) We have followed this widespread practice in proposing to include an additional five 20-mer peptides overlapping by 10 residues covering the whole protein.

Although there was not a formal statistical difference found between the two arms in the pilot study, we have selected the autologous DC vaccine platform in this study because of the statistical trend at both 24 and 48 weeks that suggested it might be better and the logistics of manufacturing a multi-epitope vaccine. All of the peptide vaccine emulsions (TARP WT27-35 and EE19-37-9V) delivered on Arm A in the 09-C-0139 study were generated manually using a syringe method of emulsification by pharmacists in the Investigational Drug Service. This approach is not logically feasible for 7 different peptides and extensive additional studies would be required to determine if peptides could be combined to generate emulsions.

The proposed phase II clinical trial is a prospective, single-blinded, randomized, placebo controlled study of 96 weeks duration in men with Stage D0 prostate cancer. Men with a PSADT  $\geq$  3 months and  $\leq$  15 months will be randomized 2:1 to receive multi-epitope TARP autologous DC vaccination or a control elutriated monocyte vaccine placebo. An initial lead-in of 6 patients will be enrolled to allow preliminary assessment of the safety of the multi-epitope TARP vaccine platform through 12 weeks before enrollment of prospectively randomized subjects blinded to treatment assignment begins.

## 2 ELIGIBILITY ASSESSMENT AND ENROLLMENT

### 2.1 ELIGIBILITY CRITERIA

#### 2.1.1 Inclusion Criteria

- 2.1.1.1 Males  $\geq$  18 years of age with histologically confirmed adenocarcinoma of the prostate. Histology confirmation must be documented with a formal pathology report. Notes from an outside physician describing the pathologic findings (based on a prior review of the full pathology report) may be used if unable to obtain the original pathology report. This will eliminate the need for an additional invasive tissue biopsy.
- 2.1.1.2 Must have completed and recovered from all prior definitive therapy (surgery, brachytherapy, cryotherapy or radiotherapy) for the primary tumor, or other definitive-intent local therapy.
- 2.1.1.3 Stage D0 disease with documented biochemical progression documented by rising PSA and no evidence of metastatic disease by physical examination, CT scan or bone scan.
- 2.1.1.4 PSADT  $\geq$  3 months and  $\leq$  15 months:
  - Patients must have  $\geq$  3 PSA measurements over  $\geq$  3 months.
  - The interval between PSA measurements must be  $\geq$  4 weeks.
- 2.1.1.5 For patients following definitive radiation therapy or cryotherapy: a rise in PSA of  $>$  2ng/mL above the nadir (per RTOG-ASSTRO consensus criteria).
- 2.1.1.6 For patients following radical prostatectomy: 2 absolute PSA values  $>$  0.2 ng/mL.

- 2.1.1.7 Non-castrate level of testosterone:  $\geq 50$  ng/dL (prior ADT allowed; must be  $\geq 6$  months since last dose of ADT).
- 2.1.1.8 Performance Status: ECOG 0-1 (Refer to [Appendix B](#)).
- 2.1.1.9 Hemoglobin  $\geq 9.0$  gm/dL, WBC  $\geq 2,500/\text{mm}^3$ , ALC  $\geq 500/\text{mm}^3$ , ANC  $\geq 1,000/\text{mm}^3$ , platelet count  $\geq 75,000/\text{mm}^3$ , and PT/PTT  $\leq 1.5X$  ULN unless receiving clinically indicated anticoagulant therapy; SGPT/SGOT  $\leq 3X$  ULN, total bilirubin  $\leq 1.5X$  ULN; creatinine  $\leq 1.5X$  ULN *and* estimated GFR (eGFR)  $\geq 60$  mL/min.
- 2.1.1.10 Hepatitis B and C negative (unless the result is consistent with prior vaccination or prior infection with full recovery); HIV negative.
- 2.1.1.11 No use of investigational agents within 4 weeks of study enrollment or use of immunosuppressive or immunomodulating agents within 8 weeks of study entry.
- 2.1.1.12 No other concurrent anticancer therapy or prior prostate cancer vaccines expressing TARP.
- 2.1.1.13 No alternative medications or nutriceuticals known to alter PSA (e.g. phytoestrogens and saw palmetto). Note: patients receiving medications for urinary symptoms such as Flomax or 5-alpha reductase inhibitors (finasteride and dutasteride) on a chronic stable dose for at least 3 months prior to study enrollment are allowed.

## 2.1.2 Exclusion Criteria

- 2.1.2.1 Patients with an active second malignancy other than adequately treated squamous or basal cell carcinoma of the skin.
- 2.1.2.2 Patients with active infection.
- 2.1.2.3 Patients on immunosuppressive therapy including:
  - Systemic corticosteroid therapy for any reason. Patients receiving inhaled or topical corticosteroids may participate.
- 2.1.2.4 Other significant or uncontrolled medical illness. Patients with a remote history of asthma or active mild asthma may participate.
- 2.1.2.5 Patients who, in the opinion of the Principal Investigator, have significant medical or psychosocial problems that warrant exclusion.

## 2.1.3 Recruitment Strategies

We anticipate accrual to this phase II to be brisk given the level of interest in our initial pilot TARP vaccination study NCI 09-C-0139. Over 220 patients were screened for HLA-A\*0201 and PSADT criteria to achieve the final accrual of 41 patients that was accomplished within 28 months. The multi-epitope (ME) TARP peptide vaccine platform covering the entire TARP protein to be used in this study eliminates the need for HLA restriction in study participants and will greatly facilitate the rate of study accrual. In addition, multiple community-based oncology providers with a substantial number of patients enrolled in the initial 09-C-0139 clinical trial have already begun referring patients in anticipation of this phase II ME TARP DC vaccine study.

In addition to the standard postings on the CCR website, as the previous Principal Investigator of the ME TARP DC vaccine study, [name] developed a brief 2-minute video that would provide an informational overview to both patients and health care providers describing the scientific rationale for and design of the clinical study.

This video would be posted to the YouTube websites of the NCI Office of Communications. Given that so much of consumer media information is now provided in video format that can easily be accessed via the web using computers and smart phone platforms, we believe that this could serve as a novel recruitment tool for patients interested in participating in clinical research studies.

Additional recruitment strategies will involve the use of flyers, posters and letters generated with the guidance of the NIH Clinical Center – Office of Patient Recruitment. Study information will be posted on NIH websites and social media forums.

## **2.2 PRE-SCREENING AND ELIGIBILITY EVALUATION**

### **2.2.1 Pre-Screening**

All potential patients must provide written documentation of outside PSA values obtained within 12 months of study entry for calculation of PSADT as outlined in **2.1.1** Inclusion Criteria. Pre-NIH calculated PSADT using the Memorial Sloane Kettering nomogram (<http://nomograms.mskcc.org/Prostate/PsaDoublingTime.aspx>) must be  $\geq$  3 months and  $\leq$  15 months for patients to be brought to the NIH Clinical Center for further eligibility screening and baseline evaluation.

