## 10 STATISTICAL SECTION

**Sample Size/Statistical Considerations:** by [name], OCD, CCR, NCI

The primary objective is to determine if the use of autologous multi-epitope TARP peptide vaccine administered using autologous dendritic cells is able to be associated with a significant difference in the rate of PSA change in patients with stage D0 prostate cancer compared to patients who receive an autologous elutriated monocyte placebo control vaccine.

After an initial run-in accrual of 6 patients to allow for preliminary assessment of ME TARP DC vaccine safety and immunogenicity, patients blinded to treatment assignment will be randomized in a 2:1 fashion between receiving ME TARP peptide autologous DC vaccine vs. autologous elutriated monocyte placebo vaccine. The primary endpoints will be the difference in the slope log (PSA) for weeks 3-24 minus that formed for the 12 months prior to enrollment on study (referred to as slope 324 – pre-slope), as well as the slope log (PSA) for weeks 3-48 vs. the same pre-treatment slope log (PSA) (referred to as slope 348 – pre-slope). As this is intended to demonstrate that at least a trend toward benefit is identified, the study will be designed using a phase 2.5 approach, in which each endpoint would be considered to have found a trend if  $p < 0.10$  from a one-tailed test. With two endpoints, the goal will be to design the study to be large enough to potentially find a difference with a 0.05 one-tailed test for each of the two endpoints in order to hold the overall error rate to 0.10.

From the prior trial of TARP peptide vaccine, the dendritic cell arm was associated with a mean  $+\text{-} \text{SD}$  slope 324 – pre-slope of  $-0.033 +\text{-} 0.072$  based on 18 patients. The slope 348 – pre-slope was  $-0.049 +\text{-} 0.062$  based on 15 patients. It is anticipated that in the absence of the vaccine

being given, that the slope 324 – pre-slope may be at least 0.010 or greater, such as 0.015, as it would be expected that the log slope (PSA) would likely very slowly increase, as a minimum, in the absence of treatment. Choosing the smaller difference would suggest that the difference in means for the two groups could be approximately -0.033 vs. +0.015, or a difference of -0.048.

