### **12.4 EVALUATION OF BENEFITS AND RISKS/DISCOMFORTS**

The potential benefit of vaccination with multi-epitope TARP peptides is unknown. Although a majority of patients (~72%) in our first 09-C-0139 TARP peptide vaccine study exhibited a decline in the slope log PSA compared to their Pre-NIH slope that was sustained out to 48 weeks, these responses were associated with absolute declines in PSA levels in only a minority of patients (~15% of responders). In addition, it is unknown and unproven whether slowing PSA velocity through vaccination or any other treatment intervention, will in turn impact clinical outcomes. Ongoing long-term observation out to 144 weeks on the 09-C-0139 study suggests that responses to TARP vaccination may wane. In addition, there were study subjects who had objective evidence of clinical progression following an initial, favorable slowing in PSA velocity. We believe that this second generation multi-epitope TARP vaccine comprised of longer synthetic peptides will include MHC class II CD4+ T cell helper epitopes that will allow generation of better CD8+ T cell responses with improved functional avidity and longevity (42) as well as humoral anti-TARP antibody responses.

TARP peptide vaccination was shown to be safe and very well tolerated in the 09-C-0139 study and we think it is highly likely that the multi-epitope TARP vaccine will have a similar, favorable safety and tolerability profile. Vaccination was also associated with induction of TARP-specific cellular immune responses in a majority of patients (~75%) as well. However the clinical significance of these immune responses remains unknown. In this study, we will attempt to definitely establish whether the observed declines in the difference in the slope log (PSA) documented in the 09-C-0139 study are real and not due to spontaneous or random slowing in the rate of PSA rise. We will also conduct an exploratory assessment of progression free survival (PFS) at 96 weeks to see if there is any indication of efficacy regarding clinical outcomes in patients receiving autologous ME TARP DC vaccination. The most significant risk for study subjects randomized to receive the autologous elutriated monocyte vaccine placebo is the apheresis required to collect cells, as autologous, minimally manipulated thawed elutriated monocytes are unlikely to be associated with any adverse reactions other than local injection site discomfort.

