### Pre-NIH and On Study PSADT Calculation:

- PSADT will be calculated using the Memorial Sloan-Kettering Cancer Center cancer information prostate nomogram for PSA doubling time found at:  
<http://nomograms.mskcc.org/Prostate/PsaDoublingTime.aspx>.
- Minimum requirements for PSADT include  $\geq 3$  PSA measurements over  $\geq 3$  months.
- The interval between PSA measurements must be  $\geq 4$  weeks.
- For patients receiving 5-alpha reductase inhibitors (5ARI) e.g. finasteride or dutasteride, only PSA values obtained after at least 3 months on therapy may be used to calculate PSADT.
- PSA values used in the calculation of PSADT must have been performed by the same laboratory, when possible.
- All PSA values used in the calculation should be  $\geq 0.2$  ng/mL and follow a rising trend although all values need not be consecutively rising.
- All values obtained over a maximum period of 12 months prior to enrollment will be utilized to calculate the patient's Pre-NIH PSADT.

Date Range of PSA Values (should not exceed 24 months): \_\_\_\_\_

Cumulative Total Months of PSA Values (should not exceed 24 months): \_\_\_\_\_

Receiving Flomax:  YES  NO      Start Date: \_\_\_\_\_ On at least 3 Months:  YES  NO

Receiving 5ARI:  YES  NO      Start Date: \_\_\_\_\_ On at least 3 Months:  YES  NO

DATE	PSA ng/mL	TESTOSTERONE ng/dL	PSADT

Record PSA values with a maximum of 2 digits after the decimal point.

NIH PSA values in blue.

Calculated Pre-Enrollment/Baseline PSADT (in months)/ Slope Log PSA: \_\_\_\_\_

Value is  $> 3.0$  Months and  $\leq 15$  Months:  YES- Eligible

NO- Ineligible for Study

**Study Number:** \_\_\_\_\_

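### The slope that admits men is also subtracted as the pre-slope, yet Section 10 plans on placebo slopes rising, so the 81% power for the 24-week endpoint is optimistic

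*Combined protocol and SAP*

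**What the plan says.** **Entry.** Section 2.2.1 states: "All potential patients must provide written documentation of outside PSA values obtained within 12 months of study entry for calculation of PSADT". It admits men whose PSADT from those values is 3 to 15 months. Section 2.1.1.4 accepts as few as three values over three months.

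**Baseline.** Appendix G states: "All values obtained over a maximum period of 12 months prior to enrollment will be utilized to calculate the patient's Pre-NIH PSADT". Its worksheet has one line, "Calculated Pre-Enrollment/Baseline PSADT (in months)/ Slope Log PSA", with the eligibility tick-box directly below it. Sections 1.1.1 and 10 subtract the slope log (PSA) of those 12 months from the on-study slope in both primary endpoints. Appendix G also wants the values to follow a rising trend. (Its worksheet allows a date range of up to 24 months, which does not match the 12-month maximum. The one value still serves both purposes.)

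**Planning.** Section 10 takes the pilot dendritic-cell arm's mean change of -0.033 (SD 0.072, 18 men) at 24 weeks and -0.049 (SD 0.062, 15 men) at 48 weeks. For untreated men it expects that "the slope 324 – pre-slope may be at least 0.010 or greater, such as 0.015". It plans on -0.033 against +0.015, a difference of 0.048, and states 81% power with 44 and 22 men. It gives no untreated value and no power for the 48-week endpoint. The placebo arm's change is used only in comparisons with the active arm.

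**Purpose.** Section 1.2.6 says the trial is to establish that the pilot declines "are indeed real and not due to spontaneous or random slowing in the rate of PSA rise". Section 12.4 repeats the aim.

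**The concern.** A slope fitted to a few PSA values carries error. Near the 15-month limit, men whose error made the slope look steep are let in, and men whose error made it look shallow are kept out. When the admitted man's slope is measured again, the error is not repeated, so his slope tends to fall without treatment. This is regression to the mean. The 3-month limit works the other way but matters less unless many screened men have short doubling times.

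The pilot used essentially the same entry window and the same baseline (Section 1.2.4), so its -0.033 may already contain such a fall. Section 10 sets that figure against a placebo value assumed to be free of it and of opposite sign. The planned difference of 0.048 is then larger than the whole pilot change, and the sample size rests on it. At stake is an overstated chance of success on the 24-week endpoint. Without a planned estimate of untreated change, it would also be hard to say afterwards how much of the pilot decline needed a vaccine to explain it.

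**Working it through.** **Inputs from Section 10.** 44 and 22 men, one-sided 0.05 per endpoint, two-group t-test with 64 degrees of freedom (critical value 1.669). Active change -0.033 (SD 0.072) at 24 weeks and -0.049 (SD 0.062) at 48 weeks.

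**Formula.** Noncentrality = difference / (SD × √(1/44 + 1/22)), with √(1/44 + 1/22) = 0.2611. The denominator is 0.0188 at 24 weeks and 0.0162 at 48 weeks.

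**The plan's figure.** 0.048 / 0.0188 = 2.55, which gives 81.1%. The stated 81% reproduces, but only with placebo at +0.015. Section 10 describes its choice as the smaller difference, but +0.015 gives 0.048 and +0.010 gives 0.043.

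**Power by placebo change, active mean held at the pilot value.** Applying the same placebo values at 48 weeks is an assumption, since the plan gives none.

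| Placebo change | 24-week difference | Noncentrality | Power | 48-week difference | Noncentrality | Power |
|---|---|---|---|---|---|---|
| +0.015 | 0.048 | 2.55 | 81% | 0.064 | 3.95 | 99% |
| +0.010 | 0.043 | 2.29 | 73% | 0.059 | 3.64 | 98% |
| 0 | 0.033 | 1.76 | 54% | 0.049 | 3.03 | 91% |
| -0.010 | 0.023 | 1.22 | 33% | 0.039 | 2.41 | 77% |

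**How far could the entry rule move untreated change?** The window is ln2/15 = 0.046 to ln2/3 = 0.231 per month, taking slopes as natural log per month. The documents give neither the PSADT distribution of screened men nor the noise in ln PSA, so both are assumed: log-normal true PSADT with log-SD 0.7, and residual SD of ln PSA from 0.05 to 0.25. True slopes are constant. Men are kept if the fitted pre-slope lies in the window, and the on-study slope uses weeks 3, 6, 9, 12, 15, 18 and 24.

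| Outside record | Mean change, median PSADT 6 to 18 months | Median PSADT 4 months |
|---|---|---|
| 5 values over 12 months | -0.0001 to -0.015 | 0 to +0.0003 |
| 4 values over 9 months | -0.0003 to -0.024 | 0 to +0.0007 |
| 4 values over 6 months | -0.0006 to -0.038 | +0.0001 to +0.002 |
| 3 values over 3 months | -0.002 to -0.070 | 0 to +0.014 |

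The fall comes from error in the pre-slope, so its expected size is the same for the 48-week endpoint.

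As a rough calibration, take the settings whose simulated SD is near the pilot's 0.072 (0.066 to 0.078) and whose median PSADT is 9 or 12 months. With four or five values the mean change is -0.006 to -0.027. With three values over three months it is -0.025 (median 9) and -0.045 (median 12).

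**Precision of a placebo-arm estimate (22 men).** The standard error at 24 weeks is 0.072/√22 = 0.0154, so the 90% CI half-width is 1.721 × 0.0154 = 0.026. At 48 weeks, 0.062/√22 = 0.0132 gives 0.023. The pilot mean has its own standard error, 0.072/√18 = 0.0170.

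**The case against.** The strongest reply is that the concurrent placebo arm is the standard remedy. Section 1.2.6 raises spontaneous slowing and proposes a randomized placebo control in answer. Both arms enter by the same rule and have the same baseline subtracted, so the expected fall cancels. This stands. A reader might infer that the primary comparison is biased or its type I error inflated. The documents do not support that.

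A reader might also infer that only a test of the placebo arm's own change can answer Section 1.2.6, and that the arm comparison would mislabel the pilot decline. That goes too far. For the new vaccine, the arm comparison is the primary answer, and nowhere does the protocol say that a null result will be read as proof that the pilot decline was spontaneous. What remains is narrower: Sections 1.2.6 and 12.4 speak of the decline seen in the pilot, which used two peptides in HLA-A*0201 men, whereas this trial tests seven peptides in all HLA types. The placebo estimate is therefore relevant supporting evidence.

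A rule that the placebo interval must exclude -0.033 or -0.049 would not be sound. It treats a mean of 18 or 15 men as a known constant and compares across trials and populations. If placebo and pilot shared one true mean, the difference between the two estimates at 24 weeks would have SD √(0.0154² + 0.0170²) = 0.0229. A 90% placebo interval would then lie wholly above the pilot mean about 13% of the time (simulated), not 5%.

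Two further replies have weight. The size of the fall rests on inputs that the documents do not give, and it vanishes at a median PSADT of 4 months. Section 1.2.4 also reports no strong association between change in slope and baseline PSADT (below 6 months or not). With longer records, the simulated correlation of pre-slope with change is only 0.01 to -0.26, so that report does not rule the effect out. With three values over three to six months it is -0.12 to -0.43, so the largest falls are harder to square with it.

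**Conclusion.** The concern holds as a planning point. One slope serves for entry and as baseline, the likely direction of untreated change under that rule is downward, and Section 10 assumes an upward minimum without mentioning the entry rule. The 24-week power of 81% falls to 54% if untreated slopes do not change and to 33% if they fall by 0.010. These figures keep the active mean at -0.033 and the SD at 0.072.

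The direction is likely, not certain. A true steepening of untreated slopes, which Section 10 expects, could offset a small fall, and a population with short doubling times would show little or none. Nor does 54% describe the trial as a whole: there are two primary endpoints, and the 48-week endpoint keeps 91% at a placebo change of 0 and 77% at -0.010 if the pilot's -0.049 and SD 0.062 hold.

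**What to change.** 1. In Section 10, remove +0.010 as a minimum. State that the entry rule may lower untreated change in both arms. Print power at placebo changes of +0.015, +0.010, 0 and -0.010 for both primary endpoints: 81%, 73%, 54% and 33% at 24 weeks, and 99%, 98%, 91% and 77% at 48 weeks.
2. In Section 10, prespecify the placebo arm's mean slope 324 – pre-slope and slope 348 – pre-slope, each with a confidence interval, as a descriptive estimate of untreated change. Attach no rule about excluding the pilot means.
3. In Sections 1.2.6 and 12.4, say that the arm comparison tests the multi-epitope vaccine, and that any statement about the pilot decline will also draw on the placebo-arm estimate.

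The cost is protocol wording and one extra estimate per endpoint from data already collected, with no added patients or visits. The downside is a less favourable power statement.
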